5.3 Follow-up visits

Wash-out period between 2 drug doses is at least 48-hrs (but could be more). All the doses have to be completed within 3 months after the first dose.

Visit V2 (=visit V1 +24h):

- **Pain assessment** using a Visual Analog Scale will be recorded at T₀+24h (+/- 1 hour). The VAS used will be the Numerical Pain Rating Scale where individuals rate their pain on a ten-point numerical scale. The scale is composed of 0 (no pain at all) to 9 (worst imaginable pain). Participants will be offered pain relief if needed in the form of simple analgesia (paracetamol).
- **Vital signs** (blood pressure, heart rate and respiratory rate) recorded at T₀+24h (+/- 1 hour).
- Blood samples for **pharmacokinetics** (*0,5 mL of venous blood in dry tube without anti-coagulant*) will be taken at T₀+24h.
- **Reaction at site of injection:** Each injection site will be checked visually for local reaction and any other complications (including redness, swelling, induration, tenderness, ecchymosis, necrosis, nerve injury, infection) at T₀+24h (+/- 1 hour). Reaction will be measured in millimetre, and time of occurrence will be recorded.
- All the **adverse events** and **concomitant treatments** are collected

Visit V3 (=2nd drug administration (must be ≥ 48 hours from V1 T₀):

- All women must have a **pregnancy test** (urine βhCG) done which must be negative to continue this visit.
- Participants medical history will be checked to ensure there are no changes since V0 visit.
- Baseline blood pressure, heart rate and respiratory rate will be recorded

- T₋₁: One blood sample will be taken for pharmacokinetics immediately prior to drug administration (0,5 mL venous blood taken in a dry tube without anti-coagulant)
- T₀: Drug Administration (PO, IV or IM) (as per randomization)
- **Pain assessment** using a Visual Analogue Scale (VAS) will be recorded immediately after drug administration and at 2 hourly intervals up to 8 hours. The VAS used will be the Numerical Pain Rating Scale where individuals rate their pain on a ten-point numerical scale. The scale is composed of 0 (no pain at all) to 9 (worst imaginable pain). The duration of any pain associated with IV or IM administration will be assessed once at 8 hours. Participants will be offered pain relief if needed in the form of simple analgesia (paracetamol).
The duration of any pain associated with IV or IM administration will be assessed once at 8 hours.
- Blood samples for **pharmacokinetics** (*0,5 mL of venous blood in dry tube without anti-coagulant*) will be taken at the following times after drug administration:
 - T₀+ 5min (only for IV route)
 - T₀+30min
 - T₀+1h
 - T₀+2h
 - T₀+3h
 - T₀+4h
 - T₀+5h
 - T₀+6h
 - T₀+8h (only for IM and PO routes)
- **Dry Blood Spot:** At one time-point (any time-point between T₀+ 5min and T₀+8h), a capillary blood sample will be taken at a finger with a lancet and a drop of blood will be placed on Mitra[®] device. An aliquot of 200µL of whole blood will be taken and aliquoted from the venous blood sample taken at the same time.
- **Reaction at site of injection:** Each injection site will be checked visually for local reaction and any other complications (including redness, swelling, induration, tenderness, ecchymosis, necrosis, nerve injury, infection) every fifteen minutes after administration for the first one hour then every two hours up to 8 hours after each injection and once at each subsequent visit. Reaction will be measured in millimetre, and time of occurrence will be recorded.

- Participants will have their **vital signs** (blood pressure, heart rate and respiratory rate) monitored and recorded at every fifteen minutes after administration for the first one hour then every two hours after drug administration.
- All the **adverse events** and **concomitant treatments** will be recorded.

Visit V4 (=visit V3 +24h):

- **Pain assessment** using a Visual Analog Scale will be recorded at T₀+24h (+/- 1 hour). The VAS used will be the Numerical Pain Rating Scale where individuals rate their pain on a ten-point numerical scale. The scale is composed of 0 (no pain at all) to 9 (worst imaginable pain). Participants will be offered pain relief if needed in the form of simple analgesia (paracetamol).
- **Vital signs** (blood pressure, heart rate and respiratory rate) recorded at T₀+24h (+/- 1 hour).
- Blood samples for **pharmacokinetics** (*0,5 mL of venous blood in dry tube without anti-coagulant*) will be taken at T₀+24h.
- **Reaction at site of injection:** Each injection site will be checked visually for local reaction and any other complications (including redness, swelling, induration, tenderness, ecchymosis, necrosis, nerve injury, infection) at T₀+24h (+/- 1 hour). Reaction will be measured in millimetre, and time of occurrence will be recorded.
- All the **adverse events** and **concomitant treatments** are collected.

Visit V5 (=3rd drug administration):

- All women must have a **pregnancy test** (urine βhCG) done which must be negative to continue this visit.
- Participants medical history will be checked to ensure there are no changes since V₀ visit.
- Baseline blood pressure, heart rate and respiratory rate will be recorded
- T₋₁: One blood sample will be taken for pharmacokinetics immediately prior to drug administration (0,5 mL venous blood taken in a dry tube without anti-coagulant)
- T₀: Drug Administration (PO, IV or IM) (as per randomization)
- **Pain assessment** using a Visual Analogue Scale (VAS) will be recorded immediately after drug administration and at 2 hourly intervals up to 8 hours. The VAS used will be the Numerical Pain Rating Scale where individuals rate their pain on a ten-point numerical scale. The scale is composed of 0 (no pain at all) to 9 (worst imaginable pain). The duration

of any pain associated with IV or IM administration will be assessed once at 8 hours. Participants will be offered pain relief if needed in the form of simple analgesia (paracetamol).

The duration of any pain associated with IV or IM administration will be assessed once at 8 hours.

- Blood samples for **pharmacokinetics** (*0,5 mL of venous blood in dry tube without anti-coagulant*) will be taken at the following times after drug administration:
 - T0+ 5min (only for IV route)
 - T0+30min
 - T0+1h
 - T0+2h
 - T0+3h
 - T0+4h
 - T0+5h
 - T0+6h
 - T0+8h (only for IM and PO routes)
- **Dry Blood Spot:** At one time-point (any time-point between T0+ 5min and T0+8h), a capillary blood sample will be taken at a finger with a lancet and a drop of blood will be placed on Mitra® device. An aliquot of 200µL of whole blood will be taken and aliquoted from the venous blood sample taken at the same time.
- **Reaction at site of injection:** Each injection site will be checked visually for local reaction and any other complications (including redness, swelling, induration, tenderness, ecchymosis, necrosis, nerve injury, infection) every fifteen minutes after administration for the first one hour then every two hours up to 8 hours after each injection and once at each subsequent visit. Reaction will be measured in millimetre, and time of occurrence will be recorded.
- Participants will have their **vital signs** (blood pressure, heart rate and respiratory rate) monitored and recorded at every fifteen minutes after administration for the first one hour then every two hours after drug administration.
- All the **adverse events** and **concomitant treatments** will be recorded.

Visit V6 (=visit V5 +24h):

- **Pain assessment** using a Visual Analog Scale will be recorded at T₀+24h (+/- 1 hour). The VAS used will be the Numerical Pain Rating Scale where individuals rate their pain on a ten-point numerical scale. The scale is composed of 0 (no pain at all) to 9 (worst imaginable pain). Participants will be offered pain relief if needed in the form of simple analgesia (paracetamol).
- **Vital signs** (blood pressure, heart rate and respiratory rate) recorded at T₀+24h (+/- 1 hour).
- Blood samples for **pharmacokinetics** (*0,5 mL of venous blood in dry tube without anti-coagulant*) will be taken at T₀+24h.
- **Reaction at site of injection:** Each injection site will be checked visually for local reaction and any other complications (including redness, swelling, induration, tenderness, ecchymosis, necrosis, nerve injury, infection) at T₀+24h (+/- 1 hour). Reaction will be measured in millimetre, and time of occurrence will be recorded.
- All the **adverse events** and **concomitant treatments** are collected.
- **Laboratory tests:**
 - Haematology tests (full blood count)
 - Renal function test (urea, creatinine and GFR)
 - Coagulation tests (fibrinogen, D-dimers, prothrombin time and partial thromboplastin time)
 - For women: pregnancy test (urine βhCG)

5.4 End of study visit

Due to the low toxicity of the molecule and its half-life ranging from 1 to 10 hours (depending on patient populations), healthy volunteers who participated in the study and received at least one administration of tranexamic acid will have a telephone follow-up after the end of the study. They will be contacted by **telephone 48 hours after the last administration** to check for any adverse events.

5.5 Expected length of participation, chronology and duration of the study.

Maximum period between screening and enrolment	7 days
Inclusion period	16 months
Duration of participation for each participant	Screen + 3x 2 days + 1 phone contact = over 3 months
Total study period	19 months

Table summarising the chronology of the study

Action	Visit V0 Screening	Visit V1 Inclusion	Visit V2 V1+24h	Visit V3	Visit V4 V3+24h	Visit V5	Visit V6 V5+24h	End of Study
Verification of Eligibility Criteria	X	X						
Signature of Informed Consent	X							
Demographic data	X							
Medical History	X							
Physical Examination, including weight and height	X							
Vital signs (including Blood pressure, heart rate, respiratory rate)	x	x	x	x	x	x	x	
Randomisation		x						
Drug Administration (PO, IM or IV)		X		X		X		
Pain (Visual Analogue Scale and duration of pain)		X	X	X	X	X	X	
Reaction at injection sites		X	X	X	X	X	X	
Laboratory Tests	X	X		X		X	X	
Haematology tests (full blood count)	x						x	
Renal function test (urea, creatinine, GFR)	x						x	
Coagulation tests (fibrinogen, D-dimers, prothrombin time and partial thromboplastin time)	x						x	
For women: pregnancy test (urine β hCG)	x	x		x		x	x	
Pharmacokinetic		X	X	X	X	X	X	
1 sample immediately prior to drug administration		x		x		x		
8 samples from T0+5min to T0+8h		x		x		x		
1 sample at T0+24h			x		x		x	
Dry Blood Spot: 1 capillary sample at any time-point between T0+5min and T0+8h and one 200 μ L whole blood aliquot of the venous sample taken at the same time		X		X		X		
Concomitant treatments	X	X	X	X	X	X	X	
Adverse Event		X	X	X	X	X	X	X
Telephone Follow-Up								X

5.6 Distinction between standard care and research

This study includes only healthy volunteers. All procedures are related to the trial.

5.7 Biological samples

5.8.1 Pharmacokinetics study

Serum PK samples: each dosage requires 0,5 ml of blood in dry tube without anticoagulant. The PK sample will then be centrifuged for 10 min at 4 000 rpm then the serum will be frozen at -20°C

The samples will be kept frozen at -20°C in the Clinical Investigation Centre of Necker Hospital. Once all the samples have been collected, they will be sent frozen to the mass spectrometry platform of the UFR Sciences de la Santé Simone Veil, University Versailles Saint Quentin, [name], France to perform the analysis under the supervision of [name].

Dry Blood Spot: for each participant, at visit 1, 3 and 5, at one time-point (any time-point between T0+ 5min and T0+8h), a capillary blood sample will be taken at a finger with a lancet and a drop of blood will be placed on Mitra® device. An aliquot of 200µL of whole blood will be taken and aliquoted from the venous blood sample taken at the same time. The filter papers will be kept at ambient temperature in the Clinical Investigation Centre of Necker Hospital during the study period. Once all the samples have been collected, they will be sent in the same time than serum PK samples to the UFR Sciences de la Santé Simone Veil, University Versailles Saint Quentin.

The inclusion number will be used to identify the sample, no identifying data will be transferred to the laboratory.

Once all analysis for this trial has been completed, all blood samples will be destroyed.

5.8 Termination and exit rules

5.8.1 Criteria and procedures for prematurely terminating the study treatment

- Temporary suspension of treatment: the investigator must document the reason for suspending and resuming the treatment in the subject's source file and the case report form (CRF)

- Premature termination of treatment, but the participant remains enrolled in the study until the end of the subject's participation: the investigator must document the reason
- Premature termination of treatment and exit from the study. The investigator must:
 - Document the reason(s)
 - Collect all endpoints at the moment the subject exits from the study, if the subject agrees
 - Schedule further follow-up visits, especially in case of a serious adverse event.

5.8.2 Criteria and procedure for premature withdrawals and exits from the study

- Participants may exit the study at any time and for any reason.
- The investigator can temporarily or permanently withdraw a participant from the study for any safety reason or if it is in the participant's best interest. For the safety of participants, if any of the following adverse events occur during the course of the trial, the investigator should permanently withdraw the participant: (1) allergic reaction to tranexamic acid (2) any thromboembolic event (3) any renal impairment (4) any visual disturbances attributed to tranexamic acid. If more than 5 patients were withdrawn from the study for safety reasons, the study would be terminated.

Participants lost to follow-up (that is, the participant cannot be located): The investigator must make every effort to reconnect with the participant (and record her/his attempts in the source file), at least to determine whether the participant is alive or dead.

If a participant exits the trial prematurely or withdraws consent, data collected prior to the date of premature exit will be used.

The case report form must list the various reasons why the subject exited or was withdrawn from the study:

- Adverse reaction
- Other medical problem
- Subject's personal reasons
- Explicit withdrawal of consent
- Lost to follow-up

5.8.3 Monitoring participants after the premature termination of treatment

In case of adverse events, the investigator must notify AP-HP and monitor the participants until the end of her/his participation in the research. If treatment is stopped prematurely due to a serious adverse event, a serious adverse event report will be sent by email ([contact]) to DRCI. The serious adverse event will be monitored until it is resolved.

5.8.4 Procedure for replacing participants

Participants who have signed a consent form but fail to meet the eligibility criteria after screening visit, will not be considered enrolled and must not be randomized or initiated on treatment. These participants will be replaced in order to have 15 randomized.

Randomized participants who have not received all three drug doses will be replaced. In this case, the replacement will be allocated to the same randomisation group.

5.8.5 Full or partial cancellation of the study

LSHTM (the sponsor), or the Competent Authority (ANSM) may prematurely discontinue all or part of the trial, temporarily or permanently, in the following situations:

- if unexpected facts or new information about the product, in light of which the objectives of the study or clinical programme are unlikely to be achieved.
- LSHTM reserves the right to permanently suspend enrolment at any time if the enrolment targets have not been met.

If the study is cancelled prematurely, AP-HP will inform the Competent Authority (ANSM) and the Institutional Review Board of its decision within 15 days, together with justification for the decision.

6 ELIGIBILITY CRITERIA

6.1 Inclusion criteria

- Adult healthy volunteers both men and non-pregnant women
- ≥ 18 - ≤ 45 -year-old
- Body mass index between ≥ 18 and ≤ 30 kg/m², and bodyweight between ≥ 50 and ≤ 100 kg
- Coagulation test results of fibrinogen, D-dimers, prothrombin time and a partial thromboplastin time within normal limits at screening

	Normal limits
fibrinogen	[1.5 - 3.5 g/L]
D-dimers	< 500 ng/mL
prothrombin time	> 70 %
partial thromboplastin time	< 1.2

- Normal renal function based on medical history and laboratory tests (laboratory test of serum creatinine should be in the range of 0.6–1.1 mg/dL for women and 0.7–1.3 mg/dL for men. Glomerular filtration rate (GFR) should be 90 mL/min/1.73m² or greater (adjusting for age, sex, weight and ethnicity)
- If a woman, must have a negative urine β -human chorionic gonadotropin (β hCG) pregnancy test at screening and inclusion visits
- Provision of signed informed consent prior to any study specific procedure
- People with public healthcare insurance

6.2 Exclusion criteria

- Previous thrombotic event or pre-existing pro-thrombotic disease
- Any history of seizures
- Any chronic or active cardiovascular or renal disease
- Planned general anaesthesia or surgery in the 3 months following inclusion
- Pregnant and/or breastfeeding
- Visual disturbance
- Haematuria
- Known allergy or contraindication to the study drugs or any of the excipients of the formulations

- Use of any prescription or non-prescription medication (including hormonal contraception) within 7 days before the first dose of the study drug is scheduled
- Inability to give informed consent
- Previous participation during the year in clinical studies compensated for an amount incompatible with participation in this study, verified by recording in the national register of subjects participating in human research trials.
- Legal criteria:
 - Patient deprived of liberty by judicial or administrative decision
 - Adult protected by law

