2.3 Hypothesis for the trial

Clinical trials with tranexamic acid have shown its efficacy in several indications and reduced mortality in trauma and postpartum haemorrhage patients when administered within 3 hours [1,2,4,5]. Our hypothesis is that the pharmacokinetics of tranexamic acid after intramuscular injection or the oral solution may be suitable for early use of this molecule in emergency situations, including in remote areas around the world where a parenteral approach is not readily available or in contexts where medical personnel are not available.

2.4 Description of the population of trial subjects and justification for the choice of subjects

Fifteen healthy volunteers will be included in an age range compatible with motherhood for women. This study in healthy volunteers will allow a description of the drug pharmacokinetics and a comparison of the three different administration routes in people without any specific medical condition. Subsequent trials will be planned in specific populations such as trauma patients or postpartum women. For these reasons, we will include in the present study both men and women, in an age range compatible with motherhood for women.

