5.2 Inclusion visit (V1)

All **inclusion and exclusion criteria** have to be checked by physician, to ensure laboratory tests done at the screening visit are within normal values and for women, the pregnancy test is negative.

If a volunteer meets all inclusion and has no exclusion criteria and s/he consents to participate, the participant is considered **enrolled**. The investigator will randomize her/him to one of six groups (see Section 4.2.1).

Visit V1 (=1st drug administration):

- All women must have a **pregnancy test** (urine β hCG) done which must be negative to continue this visit.
- Participants medical history will be checked to ensure there are no changes since V0 visit.
- Baseline blood pressure, heart rate and respiratory rate will be recorded
- T₋₁: One blood sample will be taken for pharmacokinetics immediately prior to drug administration (0,5 mL venous blood taken in a dry tube without anti-coagulant)

- T₀: Drug Administration (PO, IV or IM) (as per randomization)
- **Pain assessment** using a Visual Analogue Scale (VAS) will be recorded immediately after drug administration and at 2 hourly intervals up to 8 hours. The VAS used will be the Numerical Pain Rating Scale where individuals rate their pain on a ten-point numerical scale. The scale is composed of 0 (no pain at all) to 9 (worst imaginable pain). The duration of any pain associated with IV or IM administration will be assessed once at 8 hours. Participants will be offered pain relief if needed in the form of simple analgesia (paracetamol).
The duration of any pain associated with IV or IM administration will be assessed once at 8 hours.
- Blood samples for **pharmacokinetics** (*0,5 mL of venous blood in dry tube without anti-coagulant*) will be taken at the following times after drug administration:
 - T₀+ 5min (only for IV route)
 - T₀+30min
 - T₀+1h
 - T₀+2h
 - T₀+3h
 - T₀+4h
 - T₀+5h
 - T₀+6h
 - T₀+8h (only for IM and PO routes)
- **Dry Blood Spot:** At one time-point (any time-point between T₀+ 5min and T₀+8h), a capillary blood sample will be taken at a finger with a lancet and a drop of blood will be placed on Mitra[®] device. An aliquot of 200µL of whole blood will be taken and aliquoted from the venous blood sample taken at the same time.

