7.2 Traceability information for the investigational medicinal product

The investigational medicinal products will be purchased and managed by the Pharmacy at Necker Hospital, Paris. The lot number and expiry date of each dose of drug and the inclusion number of the participant will be recorded on a Drug Accountability Log. Date, time and name of person administering each dose will be recorded.

7.3 Authorised and prohibited treatments (medicinal, non-medicinal, surgical), including emergency medications

Prohibited Medication/Class of drug:	Usage:
Any other prescription or non-prescription medication	NA

The following medications and procedures are allowed during the study:

Rescue/Supportive Medication/Class of drug:	Usage:
Any emergency drug which would be required for volunteer care	Emergency treatment

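### Hormonal contraception is excluded for the 7 days before dose 1, but no criterion asks women of child-bearing potential to use another method (minor participant-safety gap, cheap to close)

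*Protocol*

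**What the plan says.** - **Population.** Section 2.4: "Fifteen healthy volunteers will be included in an age range compatible with motherhood for women". Section 6.1 sets the range at 18 to 45 years, for men and non-pregnant women.
- **Contraception.** Section 6.2 excludes "Use of any prescription or non-prescription medication (including hormonal contraception) within 7 days before the first dose of the study drug is scheduled". The summary repeats this. Contraception is mentioned nowhere else in the protocol as shown.
- **Pregnancy.** Section 6.2 lists "Pregnant and/or breastfeeding" as an exclusion. The matching criterion in 6.1 begins "If a woman, must have a negative urine" and asks for that test at screening and inclusion.
- **Testing before doses.** Sections 5.2 and 5.3 go further than 6.1. At V1, V3 and V5 every woman has a urine test "done which must be negative to continue this visit". Tests are also done at V0 and V6.
- **Timing.** V0 falls 1 to 7 days before V1 (5.1). Doses are at least 48 hours apart and all are given within 3 months of the first (5.3). The study ends with a telephone call 48 hours after the last dose (5.4).
- **If pregnancy occurs.** It is notified without delay (10.3.2.2.1) and followed to its end (10.3.2.4). A randomised participant who does not receive all three doses is replaced (5.8.4).
- **Other medication.** Section 7.3 lists as prohibited "Any other prescription or non-prescription medication".

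**The concern.** The protocol removes one common class of contraception and puts nothing in its place. A woman may even stop a hormonal method in order to qualify, and no criterion then asks her to use anything else. The protocol's own rules aim at giving no dose in pregnancy, since pregnancy is an exclusion and each dose depends on a negative test. A test detects pregnancy but does not prevent it, and it cannot show a conception from the last few days. Section 2.7 states that participants have no benefit, so nothing offsets an avoidable exposure. There is also a small practical cost: a pregnancy found at V3 or V5 ends dosing for that woman, and a replacement must be found in a trial that plans to enrol about one participant a month.

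This is a matter of eligibility and participant safety. It does not touch the primary endpoint, the sample size of 15 or the pharmacokinetic model. Eligibility rules belong in the protocol, so the point cannot be left to a statistical analysis plan.

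**Working it through.** The protocol gives no figure to reproduce, so the check is to set its rules side by side.

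**1. What is removed.** Hormonal contraception within 7 days before dose 1 (6.2 and summary).

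**2. What is put in its place.** Inclusion criteria (6.1), exclusion criteria (6.2), visit procedures (5.1 to 5.4) and withdrawal rules (5.8.2) were read for any requirement of a non-hormonal method, abstinence, sterility or contraceptive advice. There is none.

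**3. What the tests cover.** There are five tests (V0, V1, V3, V5, V6), and three of them (V1, V3, V5) decide whether a dose is given. A pregnancy advanced enough to turn the urine test positive is stopped before the next dose.

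**4. What the tests leave.**
- *Before a dose.* A conception more recent than the detection lag passes the test. The document does not give this lag; a range of 7 to 14 days is assumed here. V6 follows V5 by only 24 hours, so a conception missed at V5 will usually be missed at V6 as well.
- *Between doses.* A conception that V3 or V5 detects stops dosing, as intended. The cost is a replacement under 5.8.4. Data collected up to exit are kept (5.8.2), and the participant stays in the pharmacokinetic population if the Section 12.1 condition of one dose and one sample is met.

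**5. When a requirement would have to start.** V0 may be a single day before V1, which is shorter than any lag in the assumed range. A rule that began only at V0 could therefore leave most of the lag before dose 1 uncovered. A start at the last menstrual period, or about 14 days before V1 (the upper end of the assumed range), avoids this. The last-period option is reasonable because a period makes an earlier conception unlikely.

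**6. Fit with the 7-day washout.** If only non-hormonal methods counted over those 14 days, a woman on hormones until just before the washout would be rejected although she was protected, and the 7-day washout would in effect become 14 days. Hormonal use up to the start of the washout must therefore count.

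**The case against.** The strongest reply is that the protocol has chosen another way to control pregnancy: exclusion, a negative test before every dose, and notification and follow-up if one occurs. Nothing it says on this is false or contradictory, so a contraception rule on top would be a preference. It can be added that no harm is shown. Section 5.4 describes low toxicity and a half-life of 1 to 10 hours, the product summaries are listed as addenda but not shown, and the consent pages, where contraceptive advice might sit, are not in the copy reviewed.

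Much of this stands, and it fixes the grade as minor. It does not remove the point. The protocol's own rule takes away a method of contraception, testing cannot prevent a conception or show a very recent one, and advice in a consent form is not an eligibility criterion.

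Three stronger readings are tempting and are not supported:
- *That hormonal methods are barred throughout the study.* Section 7.3 read literally would say so, but Sections 5.2 and 5.3 offer paracetamol at the dosing and 24-hour visits, so the list is not applied literally. A bar after dose 1 is an inference.
- *That the 3-month span enlarges the undetected window.* Longer spacing does not lengthen the interval in which a conception escapes the test before any one dose. It only gives more time for conceptions that a later test can find.
- *That the risk can be stated as days at risk or as pregnancies.* Day counts would restate the assumed lag, and the protocol gives neither the number of women nor a conception rate.

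**Conclusion.** The gap is real and minor. Section 6.2 removes hormonal contraception before dose 1, and no criterion asks women of child-bearing potential for another method, although the protocol intends that no dose be given in pregnancy. The residual risk is small because a negative urine test precedes each dose. It consists of conceptions too recent to show and of conceptions between doses that cost a replacement.

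No numerical size can be given. The detection lag of 7 to 14 days is an assumption, used only to choose a starting point for the requirement. A reader might infer that the trial exposes women to a known fetal hazard or leaves pregnancy uncontrolled. The document shows neither.

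**What to change.** Add one criterion to Section 6.1 and its copy in the summary, along these lines: a woman of child-bearing potential must have used effective contraception or been abstinent since her last menstrual period or for about 14 days before V1, where a hormonal method counts until the existing 7-day washout begins. From then until the end-of-study telephone call she must use a non-hormonal method (for example a copper device or barrier method) or be abstinent. Surgically sterile women are exempt. State that the 14 days is an assumed detection lag.

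The history can be taken at V0, and the consent form should match if it does not already. No visit, test or systemic drug is added, so the pharmacokinetic study is unchanged. The costs are that a few women become ineligible and that the history before V1 rests on self-report. No method is fully reliable, so the line reduces the residual risk without removing it, and the test before each dose should stay.
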